8.2.3.1 PBMC immune cell subset frequencies and relationship to treatment and clinical outcomes

Serial blood samples for PBMC analyses will be collected at time points in Section 7.1, Schedule of procedures. Immune cell subsets will be measured using flow cytometry as has been previously described, or similar updated methods.^{29,30} PBMC analyses for all patients will be performed in the UCSF CIL.

Baseline levels of individual PBMC T cell and other immune cell subset components as well as change in levels on combination treatment will be explored for relationship with ORR, baseline liver function, as well as secondary efficacy endpoints (including PFS, DOR, OS) to determine if there is an association using Fisher's Exact tests.

8.2.3.2 PBMC T cell receptor (TCR) clonotype frequency and diversity and relationship to treatment and clinical outcomes

If funds are available, the frequency of individual TCR clonotypes and the diversity of overall TCR clonotype repertoire from PBMC samples will be measured by next-generation sequencing as has been previously described or by a similar, updated methodology.³¹ PBMC analyses for patients enrolled at UCSF will be performed in UCSF CIL.

The frequency of TCR clonotypes with identical sequences³¹ will be calculated by dividing the number of identical sequence reads by the total number of sequencing reads for that sample. TCR repertoire diversity will be calculated as the number of unique clonotypes comprising the top 25% of cumulative reads sorted by abundance.³¹ Baseline frequency and diversity as well as changes on combination treatment will be explored for relationship with ORR, baseline liver function, as well as secondary efficacy endpoints using Fisher's Exact tests.

PBMC TCR clonotype diversity/frequency will also be described at baseline and after starting combination therapy in Part 2 to characterize the time course of these effects and to better understand the relative impact of each study drug.

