death from any cause. For patients discontinued from study for other reasons than progression or death (see Section 5.2), PFS will be censored at the date last known to be progression-free. OS is defined as the time from the date of first dose of protocol therapy to the date of death due to any cause. Censoring will be performed using the date of last known contact for those who are alive at the time of analysis.

Median DOR, median PFS and OS will be summarized overall and according to treatment group. Kaplan-Meier medians and quartiles may be provided if data warrant. If data warrant, Kaplan-Meier quartile estimates along with the 95% CI will be calculated. Descriptive summaries including swim lane plots may also be generated depending on results.

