8.2.3 Exploratory endpoints

For exploratory endpoints, due to the small sample size in the study, descriptive statistics with mean and 95% confidence intervals will be used. Depending on funding availability, we plan to explore immunologic and genomic biomarkers (including PBMC T cell subsets and TCR frequency and diversity, tumor immune subset composition and immune infiltrates) for relationships to clinical features including etiology of liver disease, baseline liver function, and to the primary and secondary efficacy endpoints. No type I error will be adjusted for multiple endpoints. For continuous variables, descriptive statistics will include the number of non-missing values, mean, standard deviation, median, min and maximum. For categorical variables, descriptive statistics will include counts and percentages per category. For comparison between subgroups, ANOVA and t-tests will be used when appropriate to determine the association of the efficacy endpoints and the specific biomarkers. For association between biomarkers, Spearman correlations will be calculated to determine the significance of the association between the biomarkers of interest. A selection of planned analyses is described further below.

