8.2.3.3 Tumor immune infiltrates, T cell subsets, and TCR profiling

The presence and composition of tumor immune infiltrates including T cell subsets in pretreatment archival tumor sample will be explored for relationship with ORR, baseline liver function, as well as secondary efficacy endpoints (including PFS, DOR, OS, AFP response) and with tumor PD-L1 status by IHC to determine if there is a relationship using Fisher's Exact tests. Descriptive comparisons between primary and metastatic site samples and according to tumor location (e.g. liver vs. non-liver) or etiology (e.g. viral vs. nonviral), will be performed between subsets in the overall study depending on sample availability. TCR frequency and diversity may be analyzed depending on sample adequacy.

Any leftover archival material from any other tumor samples obtained on treatment or post-treatment for diagnostic purposes (e.g. if patient is determined to require palliative resection or need a biopsy to confirm progression) may be accessioned and analyzed for immune infiltration, T cell subsets, and TCR profile depending on quantity of evaluable tumor tissue available.

Tumor tissue immune cell profiling and TCR analyses will be performed in UCSF CIL depending on funding adequacy.

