8.2.3.4 Tumor and immune cell PD-L1 expression

Tumor and immune cell PD-L1 expression will be tested in batch after completion of enrollment. The proportion of subjects with archival tumor samples positive for PD-L1 or

PD-L1 and CD-45 expression by IHC will be reported along with 95% CI. For subjects with more than one tumor sample available for testing, designation as positive for PD-L1 expression will be based upon ≥1 positive sample. Concordance and rates of positivity between primary and metastatic site, tumor location (e.g. liver vs. non-liver), etiology (e.g. viral vs. nonviral), and pre-treatment, , and post-treatment samples (if available) will be described individually due to expectation of small subset/paired sample sizes. PD-L1 expression status in tumor and immune cells will be explored for association with ORR, PFS, and OS.

Tumor and IC PD-L1/CD45 analyses will be performed in UCSF CIL or other laboratory approved by Study Chair dependent upon funding and sample availability.

8.2.3.5 **AFP response**

Among patients with baseline AFP \geq 20 ng/mL, baseline AFP levels (using various cut points from literature) will be explored for association with ORR, PFS, and OS using Fisher's Exact tests or by Wilcoxon Rank-Sum test. Changes in levels on therapy will be measured as an increase by \geq 20% and \geq 50% from baseline, stable value within 20% and 50% of baseline, or decrease by \geq 20% and \geq 50% from baseline. The changes in level will be used to evaluate the predictive value for ORR, PFS, or OS.

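### Fisher's exact test (or Wilcoxon for AFP) is named to relate mostly continuous biomarkers to censored PFS and OS, which discards event times and much of the power; no log-rank or Cox method is planned

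*Combined protocol and SAP*

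**What the plan says.** Section 8.2.3.1 takes baseline levels of PBMC subsets and their change on treatment, and relates them to ORR, baseline liver function and "secondary efficacy endpoints (including PFS, DOR, OS) to determine if there is an association using Fisher's Exact tests". Section 8.2.3.2 says that TCR frequency, diversity and their changes "will be explored for relationship with ORR, baseline liver function, as well as secondary efficacy endpoints using Fisher's Exact tests". Section 8.2.3.3 treats tumor infiltrates in the same way, listing endpoints "including PFS, DOR, OS, AFP response) and with tumor PD-L1 status by IHC to determine if there is a relationship using Fisher's Exact tests". In section 8.2.3.5, baseline AFP "will be explored for association with ORR, PFS, and OS using Fisher's Exact tests or by Wilcoxon Rank-Sum test"; for AFP change it says only that "The changes in level will be used to evaluate the predictive value for ORR, PFS, or OS", with no test named. Section 8.2.3.4 relates PD-L1 status to ORR, PFS and OS, also without naming a test.

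The general text of 8.2.3 adds that "ANOVA and t-tests will be used when appropriate to determine the association of the efficacy endpoints and the specific biomarkers"; section 8.2.2 has a similar sentence. It introduces the subsections with "A selection of planned analyses is described further below".

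Section 8.2.2.4 defines PFS and OS as censored times. PFS is censored at the date last known to be progression-free for patients who leave for other reasons, and for OS "Censoring will be performed using the date of last known contact for those who are alive at the time of analysis". Kaplan-Meier summaries are optional there and are not linked to biomarkers.

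**The concern.** Fisher's exact test works on a table of counts. To use it here, the analyst must split a continuous marker into groups and replace a survival time by a yes/no status, either event by a chosen month or event ever versus never. The plan gives no marker cut-off for PBMC, TCR or infiltrates. For AFP it points to unspecified published cut-offs at baseline and to 20% and 50% bands for change. It gives no time cut-off for any marker.

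Wilcoxon on AFP has the same limit for PFS and OS. Either it compares AFP between status groups, or it ranks times and ignores censoring. ANOVA and t-tests do not handle censoring either.

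At stake is information. Relating these markers to clinical outcome is a listed exploratory objective (section 2.3) and the purpose of serial 60 mL research draws. At most 24 patients contribute, and fewer for PBMC because only UCSF patients are sampled.

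A smaller matter concerns on-treatment change. The schedule in 7.1 lists several sampling visits, but nothing says which of them defines the change.

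**Working it through.** The plan states no power, effect size or cut-off for the biomarker analyses, so there is no figure to reproduce. The check compares the named test with methods for censored data, by simulation.

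**Inputs from the documents.** Maximum n = 24 (8.4) and n = 12 in Part 2; survival follow-up of up to 2 years after treatment (4.3); expected study completion at about 60 months after a 48-month accrual period (4.5.2); median OS in cited sorafenib studies of 9.2 and 10.7 months (1.3.2).

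**Assumptions not in the documents.** Marker x standard normal; exponential survival with hazard (ln 2 / 9) × 2^x per month, that is, median 9 months and hazard ratio 2.0 per SD; censoring uniform over 6–24 or 24–36 months; marker split at its median; status at 9 months for Fisher; two-sided 5%.

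**Power, Fisher / log-rank on the same split / Cox on the continuous marker:**

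| n | Follow-up 6–24 months | Follow-up 24–36 months |
|---|---|---|
| 24 | 26 / 48 / 69% | 26 / 57 / 79% |
| 12 | 7 / 25 / 36% | 5 / 33 / 44% |

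These are Monte Carlo results, good to a point or two. The ranking is the same in both follow-up patterns.

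**Other assumptions.** With median OS 10.7 months, status at 12 months, administrative censoring at 24 months and 0–30% loss by the cut-off, n = 24 gives Fisher 19–28%, log-rank 44–54% and Cox 64–74%. At 20% loss, the ever/never form of Fisher has 20%. For PFS (5.5 months as a stand-in median, taken from the cited TTP; status at 6 months; 20% loss), the figures are 11–24%, 50% and 71%.

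**How much is only conservatism.** With no effect and n = 24, Fisher rejects 2.5% of the time and Cox 5.7%. With test size equalised (Fisher mid-p against permutation Cox), power at hazard ratio 2.0 is 32% against 66% at n = 24, and 17% against 32% at n = 12. For a weaker marker (hazard ratio 1.5, n = 24) it is 14% against 27%. The gap narrows but remains.

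**Marker shape.** If the marker acts as a threshold (hazard ratio 3 between halves, n = 24), power is Fisher 22%, log-rank 50% and Cox 45%.

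**Patients without a cell in the table.** Under 6–24 months of follow-up, 9% would be censored before 9 months and 16% before 12. With a minimum follow-up of 12 months (60 − 48 in section 4.5.2) or more, both shares are 0% apart from loss to follow-up.

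**DOR.** An ORR of 15% in 24 gives 0.15 × 24 = 3.6, about 4 responders. The smallest two-sided Fisher p in a 2-versus-2 table is 2 / C(4,2) = 2/6 = 0.33.

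**Cost of a landmark for on-treatment change.** Share with a PFS event before the visit = 1 − 0.5^(days / 30.44 / median PFS). At an assumed median of 4 months: C2D1 (day 28), 1 − 0.5^0.230 = 15%; C3D1 (day 56), 1 − 0.5^0.460 = 27%. For medians of 6 to 3 months the ranges are 10–19% and 19–35%.

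**The case against.** The strongest reply is that little depends on these analyses. They are exploratory and subject to funding, the plan is mainly descriptive, and the list of methods is called a selection, so a survival model is not excluded. At n = 12 every method is weak. All of that stands and limits the weight of the point. It does not make the named test suitable, because for PFS and OS it is the only kind of test the plan names.

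Fisher is also a sound choice for small categorical tables, such as infiltrate presence against PD-L1 status, or a marker category against ORR. That stands too.

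A reader might infer more than the documents support:

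- *That many patients cannot be placed for OS.* The 9% and 16% shares come from assuming a 6-month minimum follow-up. Sections 4.3 and 4.5.2 plan longer follow-up. The timeline in 4.5.2 does not add up (48 + 4 + 24 = 76 months, against about 60), but even its shortest reading leaves 12 months. Early censoring is mainly a matter for PFS.
- *That Fisher must have a time cut-off.* An ever/never table needs none and gives every patient a cell. It is merely weak, and it treats patients with unequal follow-up alike.
- *That false positives are inflated.* For baseline markers with censoring unrelated to the marker, Fisher is conservative.
- *That on-treatment change will produce spurious associations.* That needs change to be counted at any visit, which the plan does not say. For AFP change no test is named at all. The omission is a gap in specification, not a demonstrated bias.

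**Conclusion.** The point holds as a poor choice of method with low impact. For PFS and OS the plan names tests that ignore event times and do not handle censoring, and it names no method that does. Under the stated assumptions, Fisher at n = 24 has about half the power of log-rank on the same split and about a third of that of continuous Cox. At n = 12 the figures are about 5–7%, 25–33% and 36–44%. The sizes depend on an assumed effect, split, cut-off and follow-up, and part of the gap is Fisher's conservatism. That Fisher trails both alternatives held in every non-null scenario examined. The order of Cox and log-rank did not: it reverses for a threshold marker.

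No primary endpoint, dose decision or go/no-go rule is affected, and with these numbers any result stays hypothesis-generating.

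**What to change.** In 8.2.3.1–8.2.3.5, and where 8.2.2 and 8.2.3 mention biomarker association:

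- **PFS and OS:** Cox regression with the marker kept continuous, reported as a hazard ratio with 95% CI; log-rank for categorical markers such as PD-L1 status; Kaplan-Meier curves for display. State that Fisher, Wilcoxon, ANOVA and t-tests are not used on PFS, OS or DOR.
- **DOR:** describe patient by patient; swim-lane plots are already foreseen in 8.2.2.4.
- **ORR and PD-L1 status:** keep Fisher for categorical markers; use Wilcoxon rank-sum for continuous markers against ORR.
- **On-treatment change (minor):** pre-set one visit already scheduled, for example C2D1 or C3D1, as the landmark and count time from it. For PFS include patients alive, progression-free and sampled at that visit; for OS, patients alive and sampled. Do not count a missing sample as no change.

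No new visit or sample is needed: PBMC and AFP are already scheduled at C2D1 and C3D1. PBMC and tissue assays are to be run in batch after the study, so the wording can be fixed before those results exist. The costs are an amendment, with the approvals in 9.4 and the agreement in 12.1, and the loss of about 15–27% of patients from the PFS landmark analysis at an assumed 4-month median.

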8.2.3.3 Tumor immune infiltrates, T cell subsets, and TCR profiling

The presence and composition of tumor immune infiltrates including T cell subsets in pretreatment archival tumor sample will be explored for relationship with ORR, baseline liver function, as well as secondary efficacy endpoints (including PFS, DOR, OS, AFP response) and with tumor PD-L1 status by IHC to determine if there is a relationship using Fisher's Exact tests. Descriptive comparisons between primary and metastatic site samples and according to tumor location (e.g. liver vs. non-liver) or etiology (e.g. viral vs. nonviral), will be performed between subsets in the overall study depending on sample availability. TCR frequency and diversity may be analyzed depending on sample adequacy.

Any leftover archival material from any other tumor samples obtained on treatment or post-treatment for diagnostic purposes (e.g. if patient is determined to require palliative resection or need a biopsy to confirm progression) may be accessioned and analyzed for immune infiltration, T cell subsets, and TCR profile depending on quantity of evaluable tumor tissue available.

Tumor tissue immune cell profiling and TCR analyses will be performed in UCSF CIL depending on funding adequacy.

8.2.3.4 Tumor and immune cell PD-L1 expression

Tumor and immune cell PD-L1 expression will be tested in batch after completion of enrollment. The proportion of subjects with archival tumor samples positive for PD-L1 or

PD-L1 and CD-45 expression by IHC will be reported along with 95% CI. For subjects with more than one tumor sample available for testing, designation as positive for PD-L1 expression will be based upon ≥1 positive sample. Concordance and rates of positivity between primary and metastatic site, tumor location (e.g. liver vs. non-liver), etiology (e.g. viral vs. nonviral), and pre-treatment, , and post-treatment samples (if available) will be described individually due to expectation of small subset/paired sample sizes. PD-L1 expression status in tumor and immune cells will be explored for association with ORR, PFS, and OS.

Tumor and IC PD-L1/CD45 analyses will be performed in UCSF CIL or other laboratory approved by Study Chair dependent upon funding and sample availability.

8.2.3.5 **AFP response**

Among patients with baseline AFP \geq 20 ng/mL, baseline AFP levels (using various cut points from literature) will be explored for association with ORR, PFS, and OS using Fisher's Exact tests or by Wilcoxon Rank-Sum test. Changes in levels on therapy will be measured as an increase by \geq 20% and \geq 50% from baseline, stable value within 20% and 50% of baseline, or decrease by \geq 20% and \geq 50% from baseline. The changes in level will be used to evaluate the predictive value for ORR, PFS, or OS.

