1.5 Combination of multikinase inhibition and checkpoint inhibition

1.5.1 Combination multikinase inhibition and checkpoint inhibition preclinical rationale

One potential mechanism for primary or secondary resistance to checkpoint inhibition is immunosuppression by factors within the tumor microenvironment, such as by FOXP3+ regulatory T-cells (Tregs) and myeloid-derived suppressor cells (MDSC).¹⁸

Several preclinical studies suggest that multikinase inhibitors such as sorafenib may reduce the number of tumor infiltrating Tregs and myeloid derived suppressor cells (MDSC) as well as inhibiting their function, thereby promoting an immune antitumor response. In a syngeneic mouse model, the combination of the multikinase inhibitor, lenvatinib, plus anti-mouse PD-1 mAb showed greater growth inhibition in combination than with either agent as monotherapy, with complete tumor regressions in a subset of mice treated on combination. Re-inoculation with tumor cells did not grow any tumors in the mice with complete tumor regression, while all naïve animals grew tumors. The combination was associated with synergistic upregulation of interferon signaling-related genes; lenvatinib was associated with increased memory T cell and TH1 population compared with vehicle treatment.

In a small study of peripheral blood mononuclear cells (PBMC) derived from 20 HCC patients as well as 11 control patients, *ex vivo* incubation with sorafenib elicited dose-dependent Treg inhibition and effector T cell (Teff) activation at low doses, with Teff suppression at higher doses.²³ In PBMC samples from 19 HCC patients, sorafenib

treatment was associated with decreased frequency and absolute number of FOXP3+ Tregs along with significantly increased ratio of Teff to Treg by FACS analysis after 4 weeks of sorafenib therapy compared to baseline.²⁴ Conflicting data in human renal cell carcinoma blood samples have been reported, and the timing of these effects has not been well characterized.^{25,26}

Sorafenib therapy may also be associated with increased PD-L1 expression on tumor-infiltrating immune cells. In a study of 23 HCC patients with pre-treatment baseline tumor samples compared to tumor biopsies after progression on sorafenib, immune cell PD-L1 expression by IHC was significantly increased post sorafenib therapy.²⁷ These findings suggest PD-L1 expression as a possible mechanism of sorafenib resistance and support investigation of the combination of sorafenib plus PD-1 inhibition.

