1.6 Rationale for selected correlative analyses

1.6.1 PD-L1 expression

Tumor PD-L1 expression by IHC predicts an increased likelihood of response to immune checkpoint inhibition with PD-1 inhibitors in some cancer types.²⁸ A pooled analysis of 20 trials including 1475 patients with melanoma, non-small cell lung cancer (NSCLC), and genitourinary cancer showed a significant interaction between PD-L1 expression and response overall, with overall RR 34.1% vs. 19.9% (p<0.0001).²⁸ Response rates were significantly higher in PD-L1+ melanoma and NSCLC but no significant difference in response rate was observed according to PD-L1 status for genitourinary cancers, and a significant proportion of patients with PD-L1-negative tumors achieved tumor response to PD-1 inhibition across tumor types.

In HCC patients enrolled on CheckMate-040, 81% of patients in dose expansion had evaluable tumor samples for PD-L1 expression.⁴ Among these, approximately 20% of cases exhibited tumor staining positive for PD-L1, defined as membrane expression of PD-L1 on at least 1% of tumor cells. In this study, positive tumor PD-L1 expression was not significantly associated with response to nivolumab therapy.

Tumor and immune cell PD-L1 expression will be analyzed by immunohistochemistry (IHC) from pre-treatment baseline archival tumor samples in all patients and any post-treatment samples if obtained as part of standard clinical care. PD-L1 IHC analyses will be performed in the UCSF Cancer Immunotherapy Laboratory (CIL) or other laboratory approved by Study Chair dependent upon funding and sample availability.

1.6.2 Peripheral Blood Mononuclear Cell (PBMC) Immune Cell Subsets and TCR Clonotype Frequency and Diversity

Research blood samples will be collected from all patients enrolled at UCSF at time points listed in Section 7.1. Research blood samples will not be collected from patients enrolled at the sub-site.

Whole blood will be processed into PBMC and cryopreserved at the UCSF Cancer Immunotherapy Laboratory (CIL) for future analyses in batch after completion of study.

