2.1 Primary objectives

- 1. Part 1: Escalation Cohort: Maximum tolerated dose (MTD) of sorafenib in combination with standard dose nivolumab with Child Pugh A-B7 liver function
- 2. Part 2: Child Pugh B Expansion Cohort: Safety in patients with Child Pugh B liver function

2.2 Secondary objectives for Parts 1 and 2

- 1. Safety and tolerability of combination overall
- 2. Rate of irAE for combination overall and in patients with Child Pugh B liver function
- 3. Objective response rate (ORR) by RECIST 1.15 for overall study
- 4. ORR by RECIST 1.1 in patients with Child Pugh B liver function
- 5. Duration of response (DOR), progression free survival (PFS), and overall survival (OS) for Escalation Cohort and Child Pugh B Expansion Cohort and overall

2.3 Exploratory objectives for Parts 1 and 2

- Relationship between PBMC immune cell subset frequencies, baseline liver function, and clinical outcomes
- 2. Relationship between PBMC T cell receptor (TCR) clonotype frequency and diversity, baseline liver function, and clinical outcomes
- 3. Tumor tissue immune cell subsets and TCR clonotype frequency and diversity in pre-treatment archival tumor tissue samples

4.

- 5. Tumor and immune cell PD-L1 status in pre-treatment archival tumor tissue samples and relationship to clinical outcomes
- 6. Changes in HBV and/or HCV viral load on treatment
- 7. AFP changes on treatment and relationship to clinical outcomes
- Relationship between clinical outcomes and clinicopathologic features including race/ethnicity, etiology of liver disease including HBV/HCV status, baseline liver function, presence of cirrhosis, macrovessel invasion, extrahepatic spread, site(s) of metastatic disease, prior treatment history including prior radiation and arterial therapies

3. Investigators and other study participants

Principal Investigator: [name]

Associate Professor of Clinical Medicine

University of California, San Francisco (UCSF)

A second study site, University of California, Davis (UCD) was activated after completion of Part 1: Dose Escalation Cohort.

4. Study design

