- 7. Baseline hepatitis screening should be performed in all patients including HCV Ab, HBcAb total, HBsAg, and, in patients positive for HBcAb, HDV Ab. Prior serologic values collected within approximately 2 years may be used for screening if available. If HBcAb and/or HBsAg is positive, HBV DNA level by PCR should be monitored on treatment according to institutional standards (recommended is every 4 weeks according to treating investigator discretion) and patient should be treated with antiviral prophylaxis according to institutional practice. HCV RNA PCR should be monitored on treatment according to institutional practice. HBV DNA and HCV RNA should be checked and monitored in all cases of hepatotoxicity on treatment according to institutional standard practices.
- 8. Archival tumor samples (FFPE block when available and/or at least 10 unstained slides of approximately 10 µm thickness and at least 10 unstained slides of approximately 5 µm thickness plus a paired H&E slide) should be obtained from prior tumor sampling/diagnostic procedure(s) such as prior resection, core biopsy, or cytology/cell button when

UCSF Helen Diller Family Comprehensive Cancer Center

Version date: 03/09/2022 Protocol CC#: 174523

- available. FFPE block or slides should also be obtained from any subsequent tumor sampling which occurs during or after protocol therapy (such as repeat biopsy to confirm progression or palliative metastatectomy surgery). See Appendix 14.8.
- 9. Blood samples will be obtained in UCSF patients only for PBMC immune profiling at Screening, on Day 1 and 15 of Cycles 1 and 2, Day 1 of Cycles 3 and 7, then at SFUV1. See Appendix 14.8.
- 10. Removed.
- 11. AFP will be performed at screening, all cycles D1, at disease progression, SFVU1, and SFVU2.

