7.3.9.1 Archival tumor sample collection

In all patients, left-over diagnostic tumor block and/or slides from any tumor sampling procedure(s) (e.g. biopsy, fine needle aspiration, and/or resection specimens) performed prior to enrollment, during study treatment, and/or after treatment discontinuation due to progression will be obtained to determine tumor PD-L1 expression status, to characterize tumor immune infiltrates/T cell subsets, and (optional for UCSF patients only) to bank for future correlative analyses as part of the UCSF Hepatobiliary Tissue Bank and Registry (CC#124512) as a companion protocol to this study.

Formalin-fixed, paraffin-embedded (FFPE) tumor tissue blocks will be accessioned whenever available. In addition to blocks or if a block is not available, at least 10 unstained slides (prefer 10 μ m) plus 1 H&E slide from a tumor tissue block may be accessioned. Corresponding pathology reports from initial diagnosis and/or subsequent tumor sampling will be obtained. Specimens will be obtained from the Pathology Department for banking as soon as possible after consent and/or occurrence of post-enrollment tumor sampling and stored in the UCSF Biorepository. Correlative analyses using archival tissue samples will be performed in batch at completion of study and pending funding. See Appendix 14.8 for correlative specimen procurement and handling instructions.

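### The PD-L1 positivity rule in 8.2.3.4 has no time limit, so on- or post-treatment tissue can set a status that objective 5 confines to pre-treatment samples

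*Combined protocol and SAP*

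**What the plan says.** - **Objective.** Objective 5 in Section 2.3 reads: "Tumor and immune cell PD-L1 status in pre-treatment archival tumor tissue samples and relationship to clinical outcomes".
- **Rule.** For subjects with several samples, Section 8.2.3.4 states that "designation as positive for PD-L1 expression will be based upon ≥1 positive sample". It does not say when the sample must have been taken.
- **Use.** The same section adds that "PD-L1 expression status in tumor and immune cells will be explored for association with ORR, PFS, and OS". It also reports the proportion of subjects positive, with a 95% CI.
- **Tissue in the pool.** Section 1.6.1 has PD-L1 assayed "from pre-treatment baseline archival tumor samples in all patients and any post-treatment samples if obtained as part of standard clinical care". Section 7.3.9.1 covers sampling procedures "performed prior to enrollment, during study treatment, and/or after treatment discontinuation due to progression will be obtained to determine tumor PD-L1 expression status". Footnote 8 of the Part 2 schedule (7.1.2) says "FFPE block or slides should also be obtained from any subsequent tumor sampling which occurs during or after protocol therapy", and the Part 1 schedule has a matching footnote.
- **Effect of treatment.** Section 1.5.1 describes one study of 23 HCC patients in which "immune cell PD-L1 expression by IHC was significantly increased post sorafenib therapy".
- **Separate description.** Section 8.2.3.4 also plans to describe concordance and positivity rates individually across sites, etiologies and pre- versus post-treatment samples, because paired numbers will be small.

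**The concern.** A predictor of response and survival should be fixed before treatment starts. As written, a patient whose pre-treatment sample is negative, but who is re-biopsied later with a positive result, is counted as PD-L1 positive. This has three consequences.

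1. The reported proportion no longer estimates pre-treatment positivity. A second sample gives a second chance to be positive, even if treatment does nothing to PD-L1.
2. Whether a later sample exists depends on the clinical course. Confirming progression is a named reason for repeat biopsy, so for PFS the label can be assigned after the event it is meant to predict. For OS the bias can run the other way, because a patient must live long enough to be re-sampled. A reader of the final report could not undo either effect.
3. Section 8.2.3.3 relates tumor immune infiltrates to tumor PD-L1 status, so the undated label reaches a second exploratory analysis.

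**Working it through.** The plan gives no expected PD-L1 rate, power or sample size for this analysis, so there is no figure to reproduce. The check is first textual, then an illustration of size.

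**Text**

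- *Does the word archival limit the tissue to pre-treatment?* No. Section 8.2.3.3 speaks of "Any leftover archival material from any other tumor samples obtained on treatment or post-treatment for diagnostic purposes", and 7.3.9.1 places on-treatment and post-progression tissue under an archival heading.
- *Does the individual description of pre- and post-treatment samples cure the rule?* No. It covers concordance and positivity rates. It does not define the status that is set against ORR, PFS and OS.
- *Is the restriction left implicit throughout?* No. Section 8.2.3.3 names pre-treatment tissue when it relates infiltrates to outcome; 8.2.3.4 has no such limit.
- *Could later tissue be on hand?* Yes. PD-L1 is tested in batch after enrollment is complete.

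**Size (illustration)**

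Inputs:
- p = 0.20, baseline tumor-cell positivity, the CheckMate 040 figure in Section 1.6.1.
- n = 24, the maximum total in Section 8.4.
- f, the share of patients with later tissue: not in the documents, assumed 0.10 to 0.50.
- q, the chance that later tissue is positive when baseline is negative: not in the documents, assumed 0.10 to 0.40.

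Any-positive rate = p + (1 − p) × f × q. The share of positives that arises only through later tissue = (rate − p) / rate.

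| f | q | Rate | Expected positives of 24 | Share from later tissue |
|---|---|---|---|---|
| 0 | – | 20.0% | 4.8 | 0% |
| 0.10 | 0.10 | 20.8% | 5.0 | 4% |
| 0.10 | 0.40 | 23.2% | 5.6 | 14% |
| 0.25 | 0.10 | 22.0% | 5.3 | 9% |
| 0.25 | 0.40 | 28.0% | 6.7 | 29% |
| 0.50 | 0.10 | 24.0% | 5.8 | 17% |
| 0.50 | 0.40 | 36.0% | 8.6 | 44% |

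With no treatment effect at all, two independent samples per patient would give 1 − 0.80² = 36%.

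**Effect on the association (worst-case selection)**

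Suppose ORR is 15% (the level that 8.2.2.3 calls encouraging), baseline PD-L1 is unrelated to response, and only non-responders are re-sampled, a share f of them. Then:

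- P(positive | responder) = 0.20
- P(positive | non-responder) = 0.20 + 0.80 × f × q

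For f = 0.50 and q = 0.40, the second probability is 0.36, and overall positivity is 0.15 × 0.20 + 0.85 × 0.36 = 0.336. ORR is 0.030 / 0.336 = 8.9% in positives and 0.120 / 0.664 = 18.1% in negatives.

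For f = 0.25 and q = 0.10, the second probability is 0.22, and overall positivity is 0.030 + 0.187 = 0.217. ORR is 0.030 / 0.217 = 13.8% in positives and 0.120 / 0.783 = 15.3% in negatives.

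For f = 0.10 and q = 0.10, the second probability is 0.208, and overall positivity is 0.030 + 0.177 = 0.207. ORR is 14.5% in positives and 15.1% in negatives.

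The rule alone therefore produces an inverse association where none exists, from negligible to about nine percentage points over these assumptions.

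**The case against.** The best defense is that the objective governs. Section 2.3 says pre-treatment, inclusion criterion 3 requires pre-treatment tissue, and a sensible analyst would read 8.2.3.4 in that light. The any-positive rule also has an ordinary use: Appendix 8 asks for tissue from each discrete lesion, and Section 1.6.3 expects primary and/or metastatic samples, so many patients with several samples may have only pre-treatment ones. Later tissue is opportunistic. If only 10% of patients have it, the illustration adds 0.2 to 0.8 of a patient in 24. The analysis is exploratory and depends on funding and sample availability; no decision rests on it.

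The points about purpose, size and rank stand. The first does not settle the matter: an intention stated in 2.3 does not amend a rule in 8.2.3.4 that, followed literally, gives a different status.

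Three stronger readings are tempting and should not be drawn.

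- *Later tissue comes only from patients who progressed.* Section 1.6.3 also lists biopsy of an equivocal lesion, debulking and fiducial placement, and 7.3.9.1 includes sampling during treatment. Dependence on outcome is likely, but partial.
- *The protocol expects treatment to change PD-L1.* Section 1.5.1 says only that sorafenib may be associated with an increase, and its evidence is for immune cells, not tumor cells.
- *The reported positivity would be 28–52%.* That range comes from f = 1 with q from 0.10 to 0.40, so it holds only among patients who have a later sample. It also applies an assumed conversion rate to a tumor-cell figure.

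**Conclusion.** The point holds as a mismatch between a pre-treatment objective and a rule without a time limit. That conclusion rests on the text and needs none of the illustrative assumptions. Followed as written, 8.2.3.4 yields a status that can be set after the outcome and partly because of it, and so does not answer objective 5.

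The size is unknown, because the documents give neither a re-sampling rate nor a conversion rate. With 20% baseline positivity, 10–50% re-sampled and 10–40% conversion, the any-positive rate is about 21–36%. The distortion of ORR by PD-L1 group ranges from negligible to material, and its upper end also assumes that only non-responders are re-sampled. The consequence is limited to exploratory biomarker results in at most 24 patients. The wording should be corrected before batch testing.

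**What to change.** In Section 8.2.3.4:

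1. Define PD-L1 status, both for the reported proportion with its 95% CI and for the associations with ORR, PFS and OS, from samples taken before the first dose of protocol therapy.
2. Apply the any-positive rule only among those pre-treatment samples, for example when several lesions were sampled.
3. Keep on- and post-treatment samples for the individual or paired description already planned, and state that they do not alter a subject's status.
4. State that the PD-L1 status used in 8.2.3.3 is the same pre-treatment status.

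The cost is a wording change, with no new samples or assays. Inclusion criterion 3 already requires pre-treatment tissue, so no eligible patient should drop out for want of it. A subject whose pre-treatment tissue proves unusable should be reported as not evaluable for PD-L1 rather than classified from later tissue.
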